The primary outcome measure is a measure of RBD antibodies. We consider the dichotomous value (detectable or undetectable) for the level of statistical significance. We used an expected proportion of 30% of elderly individuals not presenting RBD antibodies in the placebo group at 6 months. Expecting that the intervention is over-the-counter and inexpensive, we calculated the sample size to detect a relative difference of 33%, with a two-sided alpha of 5% and a power of 80%; 584 participants are required. With a 15% attrition rate at 6 months, the total sample size is 688 patients.

Final analyses will begin in 2025 after database lock.

Unless otherwise specified, the alpha will be set at 0.05 for statistical significance.

12. Adverse events reporting

Taking probiotics has very few undesirable side effects, unless taken in doses higher than the recommended dosage (bloating, intestinal irritation, constipation). Side effects for probiotics (product adherence, medication intake, adverse effects) will be collected once every 2 weeks for 33 days. For the booster vaccine dose, all adverse events, such as local reactions (pain at the injection site or arm, local erythema, lymphadenopathy) and systemic reactions (fever, fatigue, headaches, joint pain, digestive issues, flu-like symptoms...) will be recorded once a week for 2 weeks. If a participant reports symptoms related to an infection, we will ask them to realize a COVID-19 test. If the participant is unable to get tested, we will provide them with a box of rapid tests for self-testing. If a participant needs to be hospitalized, data related to the hospitalization

will be collected. This process will be carried out with the utmost respect for the healthcare teams' work, aiming not to add extra workload. Various data collection methods are possible:

- From the medical records after the end of hospitalization;
- By contacting the patient after discharge by phone or email;
- We will ask the participant at the beginning of the study to inform us of their place of care if they leave their home;
- By contacting the designated reference person identified at the beginning of the study.

The monitoring committee will ensure the safety of the participants and will be notified of any serious adverse events (within 48 hours) and non-serious adverse events (one monthly report).

13. Definition of adherence and how adherence will be presented

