RBD antibodies: i) can powerfully block the binding between SARS-CoV-2 and its ACE2 receptor, and ii) are a correlate of antibodies and vaccine efficacy. The RBD antibody level will be determined by a validated ELISA test (95% sensitivity and 100% specificity). The primary outcome measure is a dichotomous measure of RBD antibodies (detectable or undetectable). The positivity threshold was defined based on the mean optical density (colorimetric reaction on blotting paper) of negative sera +3 SD. Possibly, a quantitative variable will be available.

Secondary outcomes

The Anti-N antibodies will be determined by the same procedure than for the dichotomous RBD antibody level (90% sensitivity and 95% specificity).

For the comparison of asymptomatic versus symptomatic COVID-19 cases, a subject will be classified as asymptomatic if the anti-N test confirms that the subject had COVID-19, but the subject never reported a positive COVID-19 test during the time period.

For the Ac (OS 4): we will perform a pseudotyped viral neutralization test. The S protein expressed by the vesicular stomatitis virus and HEK293 cells overexpressing ACE2 will be used. Memory B, CD4+ T, and CD8+ T lymphocytes (OS 4) will be studied by flow cytometry. B cells will be identified with appropriate markers and the S protein coupled with a fluorochrome. Memory CD4+ and CD8+ T cells will be identified following activation by the S protein with the appropriate markers.

21. Descriptives analyses of outcome measures

Detectability of Ac RBD will be described and compared between groups using chi-squared or fishers exact tests as appropriate. If quantitative RBD measures are available will be compared by intervention arm using t-test or rank sum testing as appropriate based on the distributions.

Distribution of log of score measures will be calculated for each of: Ac-n and lymphocytes B, T CD4+ et T CD8+ at inclusion and 6 months post vaccine. The distributions will be generated overall and comparatively by intervention arm using t-test or rank sum testing as appropriate based on the distributions.

22. Stratifying variables

The analysis will follow the randomization strategy. Gender and age were used as stratifying variables. We will use the same categories in the analysis.

23. Primary outcome analyses

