The primary analysis on the dichotomous criterion (Ac RBD) at three time points (baseline, 3 months, and 6 months post-vaccination) will use a GEE logistic regression model with a logistic link function for longitudinal binary data. This model will also include the stratification variables used for randomization (age group and sex). The other variables included in the model are the group (placebo vs. probiotic) and time (baseline, 3 months, and 6 months post-vaccination). The main parameter of interest in this model will be the interaction between the group and time.

Logistic regressions will also be performed for fixed time strata (3 months and 6 months) to assess the effect of the group at specific time points.

If Ac RBD as a quantitative variable is available, a GEE regression model with appropriate link function for continuous outcome will be used. Generalized linear models will be used to assess the effect of the group at specific time points (3 months and 6 months).

If there are differences in censoring by group, an additional GEE model will be used with inverse probability of censoring weights (IPCW) to assess the bias potentially induced by attrition during follow-up to 6 months. This method first estimates the probability of dropout to construct IPCWs, and then fits the GEE model with these IPCWs.

24. Secondary outcome analyses

The analysis for N antibodies at three time points between study groups will follow the approach described for RBD antibodies as a dichotomous variable.

For COVID-19 confirmed cases, a chi-squared test of independence will be used to compare the proportion of symptomatic and asymptomatic participants between the study groups. Cox proportional hazard models will be used to compare the risk of a COVID-19 outcome between the study groups, measured at six different time points.

The Ac criteria and B, CD4+ T, and CD8+ T lymphocytes are measured at baseline and 6 months post-vaccination. These criteria will be analyzed on their original log-transformed measurement scales (continuous variables). ANCOVA will be used to compare the groups at 6 months post-vaccination using the baseline measurement as a covariate. The CD4 or CD4/CD8 ratio with Ac-n (log-transformed) will be estimated using Spearman's correlation with a 95% confidence interval.

25. Adverse and Serious adverse events

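### The secondary analyses in section 24 do not carry the age and gender strata that section 22 promises: the S3 chi-squared test cannot, and the Cox model and S4 ANCOVA do not name them

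*SAP*

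**What the plan says.** Section 10 randomises 1:1 from separate tables by gender and by two age strata, 65-79 and 80-89. Section 22 then gives a rule that is not confined to any one outcome: "The analysis will follow the randomization strategy. Gender and age were used as stratifying variables". It adds that the analysis will keep the same categories.

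Section 23 applies the rule by naming age group and sex as terms in the GEE for RBD antibodies. Section 24 has the anti-N analysis follow the same approach, so S2 inherits them.

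The other analyses in section 24 read differently:

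- **S3, proportions.** For confirmed COVID-19 cases, "a chi-squared test of independence will be used to compare the proportion of symptomatic and asymptomatic participants between the study groups".
- **S3, risk over time.** "Cox proportional hazard models will be used to compare the risk of a COVID-19 outcome between the study groups". No covariate or stratum is named.
- **S4, antibodies and lymphocytes.** "ANCOVA will be used to compare the groups at 6 months post-vaccination using the baseline measurement as a covariate". Section 9 limits this analysis to a selected subsample of 100.

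**The concern.** After stratified randomisation, the strata belong in the analysis if they predict the outcome. Leaving them out gives up precision that the design has made available. Here the SAP states that principle, applies it to two outcomes, and then specifies the rest in terms that do not include it.

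Two things are at stake. One is a modest loss of efficiency, felt most in S4 because that subsample is small. The other is an open choice: two statisticians could follow this SAP faithfully and fit different models for the Cox and S4 analyses, one adjusted and one not. That choice should be closed before the allocation is disclosed.

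**Working it through.** **The plan's own figure.** The SAP gives no power or sample size for S3 or S4, only for the primary outcome: "We used an expected proportion of 30% of elderly individuals not presenting RBD antibodies in the placebo group at 6 months", and "a relative difference of 33%, with a two-sided alpha of 5% and a power of 80%; 584 participants are required". With 30% against 20%:

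- Unpooled: (1.96 + 0.8416)² × (0.30 × 0.70 + 0.20 × 0.80) / 0.10² = 7.849 × 0.37 / 0.01 = 290.4, so 291 per arm, 582 in all.
- Pooled variance: 294 per arm, 588 in all.
- Attrition: 584 / 0.85 = 687.1, and 688 as an even total.

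The stated 584 lies between the two formulas and gives 79.8% power, so it reproduces. It does not bear on the secondary analyses beyond fixing the size of the trial.

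**Inputs for the secondary analyses.** From the SAP: 1:1 allocation, two age strata by gender (section 10), 100 in S4 (section 9), default alpha 0.05 (section 11; taken as two-sided, as in the sample size). Not in the SAP, so assumed: how strongly age group and sex predict the outcomes; 15% of participants aged 80-89; 50% women.

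**S4 ANCOVA.** Without strata the model has an intercept, group and baseline value, leaving n - 3 degrees of freedom. With age group and sex it has n - 5. If the strata explain a share R² of the residual variance and are balanced between arms:

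SE ratio (with / without) = √[(1 - R²)(n - 3)/(n - 5)]

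Power with strata = Φ(2.8016 / ratio - 1.96), for a test with 80% power without them. With n = 100:

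| R² | SE ratio | Power with strata |
|---|---|---|
| 0% | 1.0105 | 79.2% |
| 2% | 1.0003 | 80.0% |
| 5% | 0.9849 | 81.2% |
| 10% | 0.9586 | 83.2% |

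Break-even is at R² = 1 - 95/97 = 2.1%. With 85 completers (100 less 15%), the 10% row becomes 0.9605 and 83.1%.

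A simulation of 1,500 runs per setting agrees. At R² = 10%, power without and with strata was 80.0% and 83.6% when the 100 were block-randomised within strata, and 79.3% and 81.9% when they were a random subsample of a larger stratified trial.

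**S3 Cox model.** Simulation with n = 584, treatment hazard ratio 0.67 (log -0.400), and age group and sex each carrying the hazard ratio shown, fitted without and then with both as covariates:

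| Strata HR | Log HR without / with | SE without / with | Power without / with |
|---|---|---|---|
| 1.0 | -0.388 / -0.389 | 0.1796 / 0.1796 | 57.4% / 57.6% |
| 1.5 | -0.399 / -0.404 | 0.1586 / 0.1587 | 69.1% / 70.1% |
| 2.0 | -0.390 / -0.406 | 0.1449 / 0.1451 | 77.6% / 80.1% |

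The standard error does not move. The loss comes from a log hazard ratio pulled toward zero. With 1,500 runs, the Monte Carlo error of a single power figure is √(0.8 × 0.2 / 1500), about 1 point.

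**Type I error.** Without strata, null rejection was between 3.8% and 5.1% across the ANCOVA and Cox settings: at or slightly below nominal.

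**S3 chi-squared test.** No calculation can be tied to the plan. The test is worded for confirmed cases, and the SAP does not say how many are expected.

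**The case against.** **Silence is not exclusion.** Section 22 is unrestricted, and nothing in section 24 rules the strata out of the Cox model or the ANCOVA. Naming the baseline value as a covariate does not say it is the only one. The fixed-time logistic regressions in section 23 do not repeat the strata either. This stands: for these two models the text is ambiguous rather than contradictory. It does not dispose of the point, because section 23 does name the strata for its main model and section 24 does not. Nor does it help the chi-squared test, which cannot take them on any reading.

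**A reader might infer that the standard errors are too wide in all three analyses.** The documents do not support that. In the Cox model the standard error is unchanged. In the ANCOVA, a model standard error larger than the true variability requires strata balanced between arms. The SAP states no blocking method and says only that the 100 were selected. In the simulated random subsample the unadjusted standard error (0.201-0.202) was close to the empirical standard deviation (0.193-0.204): efficiency was lost, but the standard error was not clearly overstated.

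**A reader might also put a number on the S3 loss** by treating the whole trial as the denominator, about 620 people (688 × 0.902) with assumed infection risks by age. The wording for confirmed cases points to a post-randomisation subset of unknown size, in which balance is not assured. Such a figure is illustrative at best.

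**The effect is small and rests on assumptions.** This stands too. If age and sex add nothing beyond the baseline value, adjustment costs the ANCOVA about 1 power point rather than gaining any.

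**Conclusion.** The inconsistency is real. It is a direct conflict with section 22 for the chi-squared test, and an unresolved silence for the Cox model and the ANCOVA. The statistical cost is minor and conservative: no false-positive risk, secondary analyses only.

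The sizes in the ANCOVA and Cox tables depend on prognostic strengths that the SAP does not give. The Cox shrinkage is relative to the within-stratum hazard ratio, since adjusting for a prognostic factor changes what the hazard ratio measures. For S4 there is the further point that chance differences in age or sex between arms, in a subsample whose balance is not stated, would go uncorrected. The S3 loss remains unquantified.

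The case for acting rests on consistency and on fixing the model in advance, more than on the power recovered.

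**What to change.** Amend section 24 before the allocation is disclosed, and log the change in the section 5 table:

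- (a) Replace the chi-squared test with a Cochran-Mantel-Haenszel test over the age group by gender cells, or a logistic model including both factors.
- (b) State that the Cox model is stratified by, or adjusted for, age group and sex. Choose one.
- (c) Add age group and sex to each S4 ANCOVA, alongside the baseline measurement.

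The cost is three sentences and two degrees of freedom in each ANCOVA. The strata are already recorded for every participant, so no new data are needed. Adding further covariates, such as baseline anti-N in the Cox model, is a separate matter that section 22 does not call for.

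If the sponsor prefers unadjusted secondary analyses, section 22 should be limited explicitly to the primary and anti-N analyses. That removes the contradiction but not the small efficiency loss.
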